13. REGULATORY CONSIDERATIONS

13.1. Protocol Review and Amendments

This protocol, the proposed informed consent and all forms of participant information related to the study (e.g., advertisements used to recruit participants) and any other necessary documents must be submitted, reviewed, and approved by a properly constituted IRB. All decisions of the IRB concerning the conduct of the study must be made in writing.

Any changes made to the protocol must be submitted as amendments and must be approved by the IRB prior to implementation. Any changes in study conduct must be reported to the IRB.

Additionally, the DoD (Department of Defense)/OHRO (Office of Human Research Oversight) must approve ALL substantive modifications to the protocol and any modifications that could potentially increase risk to participants prior to implementation. OHRO defines a substantive modification as a change in Principal Investigator, change or addition of an institution, elimination or alteration of the consent process, change in the IRB of Record, change to the study population that has regulatory implications (e.g. adding children, adding active duty population, etc.), significant change in study design (i.e. would prompt additional scientific review), or a change that could potentially increase risks to participants.

The NF Clinical Trials Consortium (NFCTC) Operation Center will disseminate protocol amendment information to all participating investigators.

13.2. Informed Consent

All participants must be provided a consent form describing this study and providing sufficient information for participants to make an informed decision about their participation in this study.

The formal consent of a participant, using the IRB-approved consent form, must be obtained before the participant is involved in any study-related procedure. The consent form must be signed and dated by the participant or the participant's legally authorized representative, and by

the person obtaining the consent. The participant must be given a copy of the signed and dated consent document. The original signed copy of the consent document must be retained in the medical record or research file.

13.3. Ethics and Good Clinical Practice (GCP)

This study is to be conducted according to the following considerations, which represent good and sound research practice:

- E6 Good Clinical Practice: Consolidated Guidance
<https://www.fda.gov/media/93884/download>
- US Code of Federal Regulations (CFR) governing clinical study conduct and ethical principles that have their origin in the Declaration of Helsinki
 - Title 21 Part 11 – Electronic Records; Electronic Signatures
<https://www.accessdata.fda.gov/scripts/cdrh/cfdocs/cfcfr/CFRSearch.cfm?CFRPart=11>
 - Title 21 Part 50 – Protection of Human Subjects
<https://www.accessdata.fda.gov/scripts/cdrh/cfdocs/cfcfr/CFRSearch.cfm?CFRPart=50>
 - Title 21 Part 54 – Financial Disclosure by Clinical Investigators
www.access.gpo.gov/nara/cfr/waisidx_02/21cfr54_02.html
 - Title 21 Part 56 – Institutional Review Boards
<https://www.accessdata.fda.gov/scripts/cdrh/cfdocs/cfcfr/CFRSearch.cfm?CFRPart=56>
 - Title 21 Part 312 – Investigational New Drug Application
<https://www.accessdata.fda.gov/scripts/cdrh/cfdocs/cfcfr/CFRSearch.cfm?CFRPart=312>
- State laws
- It is understood that deviations from the protocol should be avoided, except when necessary to eliminate an immediate hazard to a research participant. In such case, the deviation must be reported to the IRB according to the local reporting policy.

13.4. Data Collection

The trial is being conducted by the NFCT Consortium. Case report forms developed by the NFCTC Operations Center and Protocol Chair will be used for submitting clinical data to the Operations Center. Data must be submitted to the Operations Center within two weeks of completing each required evaluation while the subject is on study via eDCS. Delinquent data delays will be reported to the NFCT Consortium's Site Evaluation Committee and the NFCTC Operations Center.

Completed QOL and pain evaluations will be submitted in real-time via an iPad and NIH Toolbox to the NFCTC Data Coordinating Center.

Blood and tissue samples for banking will be handled and stored in the biorepository located in the Colket Translational Research Building at the Children's Hospital of Philadelphia (CHOP), Philadelphia, PA. The specimens will be under the management of the Center for Data Driven Discovery in Biomedicine (D3b) and the Biorepository Core (BioRC), according to their standard operating procedures (SOPs). Samples will be stored at -80°C. Biological specimens will be coded with a randomly generated study number prior to shipping to the biorepository in order to prevent identification of subjects and protect confidentiality. The study number will not be derived from or related to information about the subject and will not contain any elements of PHI. The specimen number will be entered into the NFCTC Operations Center eDCS, thus providing a link between the specimen and the study data. Specimens may be shared with outside investigators/laboratories, who may analyze (and store, if applicable) the samples. Shared specimens will be labeled only with a study number. Requests for samples will be reviewed by the NF111 Study Chairs and the NFCTC Biology Committee. If a subject withdraws consent to store samples after collection, existing samples in the biorepository will be destroyed; however, any samples already shared to an outside laboratory or other entity will not be destroyed and any data generated already from the samples will not be destroyed.

13.5. Study Documentation

The investigator must prepare and maintain adequate and accurate case histories designed to record all observations and other data pertinent to the study for each research participant. This information enables the study to be fully documented and the study data to be subsequently verified.

Original source documents supporting entries in the case report forms include but are not limited to hospital records, clinical charts, laboratory and pharmacy records, recorded data from automated instruments, microfiches, photographic negatives, microfilm or magnetic media, and/or x-rays.

13.6. Records Retention

All study-related documents must be retained for the maximum period required by applicable federal regulations and guidelines or institutional policies. Study-related documents will be stored in a secured location accessible only to the investigators and formally designated study personnel.

13.7. Multi-Center Guidelines

This protocol will adhere to the policies and requirements of NFCTC IRB, DoD and the Sponsor. The specific responsibilities of the Protocol Chair, NFCTC Operations Center, and Participating Institutions are presented in the Multi-Center Data and Safety Monitoring Plan.

- The Protocol Chair and NFCTC Operations Center are responsible for distributing all IND Action Letters or Safety Reports to all participating institutions for submission to their individual IRBs for action as required.
- Mechanisms will be in place to ensure quality assurance, protocol compliance, and adverse event reporting at each site.

13.8. Publication of Data and Protection of Trade Secrets

The Principal Investigator (Protocol Chair) holds the primary responsibility for publication of the study results; provided that the PI will provide any such publication to Oncovir, Inc. for review at least sixty (60) days prior to submission and also comply with any provisions regarding publication as are agreed to between the Neurofibromatosis Clinical Trials Consortium and Oncovir, Inc. in the Clinical Trial Agreement related to this study. The results will be made public within 13 months of the end of data collection.

However, if a report is planned to be published in a peer-reviewed journal, then that initial release may be an abstract that meets the requirements of the International Committee of Medical Journal Editors. In any event, a full report of the outcomes should be made public no later than three (3) years after the end of data collection. Authorship for abstracts and manuscripts resulting from this study will be determined according to guidelines established by the International Committee of Medical Journal Editors.

14. STATISTICAL CONSIDERATIONS

Primary Endpoints

The primary endpoint of the study is objective response rate (defined as CR or PR) during the first 12 months of treatment. Response will be assessed through the time of the post-12th cycle tumor assessment, or through the last tumor assessment time during this nominal period for patients in follow-up but who have withdrawn from protocol therapy, or through the last available tumor assessment for patients who are lost to follow-up during this time.

The percent change in tumor sizes compared to baseline will be recorded at each evaluation time and will be used to define the categorical response as described below, per the definition of CR, PR, MR, SD, and PD in section 10.4.

- For tumors that regress compared to baseline during the assessment period without first satisfying the criteria for progressive disease (PD), response will be defined at the nadir of the tumor size compared to baseline provided that the percent reduction at the nadir satisfies the definition of CR, PR, or MR per section 10, with the response value of CR, PR, or MR determined by the percent reduction at this time.

The associated time of response will also be recorded.

- For tumors that progress compared to baseline and satisfy the definition of PD without first satisfying the criterion at least for minor response (MR), response will be defined at the first time at which the percent increase in tumor size compared to baseline satisfies the criterion for PD. The response value will be PD. The associated time of response will also be recorded. Progressive disease could be confirmed with a short follow-up MRI (+/- 6 weeks) per treating physician decision, otherwise continue with MRI interval per protocol.
- For tumors that neither regress sufficiently to satisfy the criterion for MR nor progress sufficiently to satisfy the criterion for PD during the assessment period, the response value will be determined to be SD.

Patients will be considered evaluable for response if they have received at least one dose of treatment and have at least one post-baseline tumor assessment.

Patients who undergo gross total resection while on study will be excluded from further response at the time of surgery. Patients who have measurable residual disease (at least twice the thickness of the MRI slide) after resection will be able to continue study drug and the post-op MRI will be used as the new baseline.

Secondary Endpoints

- Progression free survival (PFS), defined as the time from start of treatment to the first occurrence of tumor recurrence, tumor progression, occurrence of a second malignancy, or death from any cause. Patients event-free at last follow-up will be censored in analysis. PFS will be determined at 12, 24 and 60 months.
- Objective response rate (defined as CR or PR) after 24 cycles of treatment. Response will be assessed through the time of the post-24th cycle tumor assessment, or through the last tumor assessment time during this nominal period for patients in follow-up, but who have withdrawn from protocol therapy, or through the last available tumor assessment for patients who are lost to follow-up during this time.
- Clinical benefit defined as (CR+PR+MR+SD). Clinical benefit will be assessed through the time of the post-12 and 24th cycle tumor assessment, or through the last tumor assessment time during this nominal period for patients in follow-up but who have withdrawn from protocol therapy, or through the last available tumor assessment for patients who are lost to follow-up during this time.
- The grade and duration of CTCAE toxicities observed during treatment using CTAE version 5.0.
- Evaluation for visual acuity for patients with optic pathways gliomas will be assessed at 12 months and 24 months from starting therapy. Patient visual outcome will be assessed through the time of the post-12th and 24th cycle visual assessment, or through the last visual assessment time during this nominal period for patients in follow-up but who have withdrawn from protocol therapy, or through the last available tumor assessment for patients who are lost to follow-up during this time.

Exploratory Endpoint

The RANO criteria for response assessment will be determined and descriptively compared to the primary response using RAPNO.

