3.5. Criteria for Removal from Protocol Therapy and Off Study Criteria

Removal from Protocol Therapy

The following are criteria for removal from protocol therapy:

- a) Confirmed progressive disease (clinical or radiographic).
- b) Completion of cycle 24.
- c) Poly-ICLC related toxicity requiring removal.
- d) Participant has not received drug (for any reason) for greater than 28 days.
- e) Refusal of further protocol therapy by participant/parent/guardian.
- f) Another tumor develops that requires non-surgical therapy (e.g. chemotherapy, radiation etc;).
- g) Non-compliance, that in the opinion of the investigator does not allow for on-going participation.
- h) Physician determines it is not in the participant's best interest.
- i) Participant has complete resection of target lesion and there is no evidence of residual disease.
- j) Participant becomes pregnant.
 - If a participant becomes pregnant while receiving investigational therapy or within 90 days after the last dose of study drug, the participant should be followed until the outcome of the pregnancy.

Participants who are off protocol therapy are to be followed until they meet the criteria for OFF Study (see below).

Off-Study Criteria:

- Completion of their 5 year follow-up MRI scan
- Participant starts new tumor-directed therapy
- Death
- Lost to follow-up
- Withdrawal of consent for any further data submission

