10.4. Imaging Response Assessment

The overall response assessment takes into account response in the target lesion ONLY. The response in the non-target lesions will be evaluated independently from the response for the TARGET lesion.

Note: Participants with a global deterioration of health status requiring discontinuation of treatment without objective evidence of disease progression at that time should be reported as "*symptomatic deterioration*." Every effort should be made to document the objective progression even after discontinuation of treatment.

Evaluation of Target Lesion

- **Complete Response (CR)** Complete disappearance of the target lesion on T2 weighted and T2 weighted fluid attenuated inversion recovery (FLAIR) imaging and contrast imaging using baseline MRI or best recorded response for comparison. Overall, the patient must be clinically stable or have improved on physical examination and functional or neurological assessment.
- **Partial Response (PR):** a 50% or greater reduction in the target lesion on T2 weighted and T2 weighted-FLAIR imaging using the baseline MRI for comparison. Overall, the patient must be clinically stable or have improved on physical examination and functional or neurological assessment.
- **Minor Response (MR):** a 25-49% reduction in the target lesion on T2-weighted and T2-weighted-fluid-attenuated inversion recovery imaging using the baseline MRI or best recorded response for comparison. Overall, the patient must be clinically stable or have improved on physical examination and functional or neurological assessment.
- **Stable Disease (SD):** An increase or a decrease in the target lesion that is not sufficient to qualify as progressive disease or responsive disease (partial response or minor response), respectively. Overall, the patient must be clinically stable or have improved on physical examination and functional or neurological assessment.
- **Progressive Disease (PD):** A greater than 25% increase in the target lesion, usually assessed on T2-weighted and T2-weighted FLAIR using the baseline MRI or best recorded response for comparison. A determination of PD may be deferred if pseudoprogression is suspected (see "**Consideration for possible pseudoprogression / treatment-related effect**" below). Given the possibility of pseudoprogression with immunotherapy, a short interval MRI at the discretion of the treating physician is recommended for participants with PD.

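### Section 14 assigns stable disease on tumor size alone, so a patient removed for confirmed visual or clinical progression with a size-stable lesion can count as clinical benefit

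*Combined protocol and SAP*

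**What the plan says.** Section 14 (Primary Endpoints) uses percent change in tumor size from baseline to define the response category, "per the definition of CR, PR, MR, SD, and PD in section 10.4". Three bullets follow.

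- Shrinkage: response is taken at the nadir, provided that the reduction there meets the CR, PR or MR definition in Section 10. The value is "determined by the percent reduction at this time".
- Progression: "response will be defined at the first time at which the percent increase in tumor size compared to baseline satisfies the criterion for PD".
- Everything else: tumors that "neither regress sufficiently to satisfy the criterion for MR nor progress sufficiently to satisfy the criterion for PD during the assessment period" are SD. This bullet has no clinical or visual condition.

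Section 10.4 attaches one sentence to each of CR, PR, MR and SD: "Overall, the patient must be clinically stable or have improved on physical examination and functional or neurological assessment". Its PD sentence is an increase of more than 25% in the target lesion. Notes below it refer to 9.5 for visual progressive disease and mention progression by clinical criteria, but do not say how either enters the response category. A separate note has global deterioration that stops treatment, without objective progression, reported as symptomatic deterioration.

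Section 9.5 defines visual progressive disease as worsening of at least 0.2 logMAR. Its footnote deals with the first on-therapy evaluation when the tumor is stable or smaller on MRI, and ends in removal if a second exam confirms further worsening. Section 3.5(a) lists confirmed progression, clinical as well as radiographic, as a reason for removal.

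Under Secondary Endpoints, Section 14 defines clinical benefit as CR+PR+MR+SD through the post-12 and post-24 cycle assessments. Patients who have left therapy but remain in follow-up are scored through their last tumor assessment in the period.

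**The concern.** Two parts of the plan that should describe one scoring rule do not give the same answer for one kind of patient: lesion size steady, vision or clinical state confirmed worse, drug stopped for progression. Section 10.4 will not let this patient be SD. The Section 14 bullet makes the patient SD by default, because SD is whatever remains after the size tests for MR and PD.

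At stake is the meaning of the clinical benefit rate. A patient taken off drug because the disease progressed could be reported as having benefited from it. The situation can be foreseen: optic pathway patients have acuity tested every three cycles, and the 9.5 footnote is written for visual worsening with a stable or smaller tumor. Section 10.6 describes an imaging review at the end of the trial and does not say that examination or acuity findings are supplied to it, so nothing there would correct a size-only score.

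**Working it through.** **Step 1. Reproduce the plan's own figures (Section 14.2).** Inputs: n = 16, success if at least 3 respond, P0 = 0.05, P1 = 0.25. With X binomial:

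- alpha = P(X ≥ 3 | 16, 0.05) = 1 − (0.4401 + 0.3706 + 0.1463) = 0.0429. The plan states 0.043.
- beta = P(X ≤ 2 | 16, 0.25) = 0.0100 + 0.0535 + 0.1336 = 0.1971. The plan states 0.197. Power is 0.8029.

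The design reproduces. Section 14.3 classifies patients as CR/PR versus MR/SD/PD, so moving a patient between SD and PD leaves the responder count, and this test, unchanged.

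**Step 2. Apply each rule to one patient.** Take an optic pathway patient whose target lesion never shrinks by 25% or more and never grows by more than 25%. Visual worsening beyond 0.2 logMAR is confirmed by a second exam, and the patient is removed.

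| Rule | Result |
|---|---|
| 10.4, CR, PR or MR | No: shrinkage too small |
| 10.4, SD | No: the clinical condition fails |
| 10.4, PD sentence | No: growth does not exceed 25% |
| 10.4 notes and 9.5 | Visual progressive disease, with no stated response category |
| Section 14, PD bullet | No: the size criterion is not met |
| Section 14, SD bullet | SD |
| Section 14, clinical benefit | Counted as benefit |

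The 10.4 category for unevaluable disease does not help either, because the lesion can be measured.

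A variant arises if the patient first reaches MR while clinically stable and then progresses visually. The nadir bullet keeps MR, and MR also counts as benefit.

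**Step 3. Size.** Change in the clinical benefit rate per patient = 1/n.

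- n = 16: 1/16 = 6.25 points.
- n = 20 (all enrolled patients evaluable): 1/20 = 5 points.

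The documents give no expected clinical benefit rate and no expected number of such patients. As an illustration only, assume that 12 of 16 count as benefit under the size-only rule, and move 0 to 4 of them to no benefit (exact 95% confidence intervals):

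| Patients moved | Rate | 95% CI |
|---|---|---|
| 0 | 75.0% | 47.6 to 92.7 |
| 1 | 68.8% | 41.3 to 89.0 |
| 2 | 62.5% | 35.4 to 84.8 |
| 3 | 56.3% | 29.9 to 80.2 |
| 4 | 50.0% | 24.7 to 75.3 |

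**The case against.** The best defense is that Section 14 says its categories follow 10.4. On that reading 10.4 supplies the definitions, including the clinical condition, and the bullets only fix the timing: nadir, first progression, or neither. For CR, PR and MR this is a strong argument, because the nadir bullet itself requires that the Section 10 definition be met. It is weaker for SD, whose bullet has no such proviso and is worded as a remainder. Importing 10.4 also does not finish the job. It removes the patient from SD without placing the patient in PD, because 10.4's PD sentence is about size.

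A reader might infer that the primary result is exposed: a 50% shrinkage with clinical worsening scored as PR could turn 2 of 16 into 3 of 16. The documents do not support that as an established flaw. The nadir bullet's proviso arguably already excludes such a PR, and SD versus PD is irrelevant to the primary test.

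Three further points stand. No frequency is given, and visual worsening as an entry criterion describes patients before treatment, not the rate on treatment. Clinical benefit is a secondary rate with no hypothesis test, in a plan that calls its analyses largely descriptive. Visual acuity outcome is reported separately, so visual worsening would not vanish from the report. These limit the consequence; they do not settle how the patient is counted.

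**Conclusion.** The point holds for the SD bullet and the clinical benefit rate. Read literally, Section 14 counts as benefit a patient whom 10.4 would not call SD and whom 9.5 or 3.5(a) removes for progression; read through its cross-reference, it leaves that patient without a category. Either way the secondary endpoint at 12 and 24 cycles is not fully defined.

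The size is 6.25 points per patient at n = 16 and 5 points at n = 20. The total effect is unknown because the number of such patients is unknown, and it could be zero. The sample size, the cut-off of 3, alpha 0.0429 and power 0.8029 are unaffected. The conclusion assumes that an analyst would apply the SD bullet as written. It does not assert that CR, PR or MR are mis-scored. This should be corrected before responses are scored, but it does not threaten the primary decision.

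**What to change.** Reconcile Section 14 with 10.4 by adding the following:

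1. CR, PR, MR and SD each require the 10.4 clinical-stability condition at that assessment.
2. For the clinical benefit rate, a patient with confirmed visual or clinical progression, as already defined in 9.5 and 3.5(a), by the 12- or 24-cycle time point is counted as not having clinical benefit. This applies whatever the tumor size and also after an earlier MR. The progression date is taken as 9.5 dates it.
3. A statement of how symptomatic deterioration under 10.4 is counted in that rate.

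The cost is a few sentences. No removal or treatment rule changes, and the sample size and decision rule stay as they are. The downside is that the clinical benefit rate may be slightly lower.

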14.2. Sample Size

Target is 20 patients for 16 evaluable participants.

To allow for 25% unevaluable participants, a maximum of up to 20 participants will be enrolled. We anticipate enrollment to be completed in 36 months with primary outcome measure defined in 12 months. The sample size for this trial is based on 3 primary factors: safety based on risk versus benefit. Sample size estimates were based on a single stage phase II clinical trial with the goal of demonstrating that the objective response rate of poly-ICLC is better than an objective response rate of a *poor* drug. For the sample size calculation, we assumed that the response rate of a poor drug (P_0) was 5% (i.e., $P_0 = 5\%$) and that the objective response rate poly-ICLC (P) would be at least 25% (i.e., $P = 25\%$).

In addition, the type I error rate (alpha) was set to 0.05 (5%) and the type II error rate ($\beta = 1 - \text{power}$) was set to 0.20 (20%). Using a single stage design, a sample size of 16 participants achieves at least 80% power to demonstrate that the objective response rate of poly-ICLC is better than a poor objective response rate of 5% and at least 25%. If the number of responders is 3 or more, the hypothesis that $P \leq 5\%$ is rejected with an actual error rate of 0.043. If the number of responses is 2 or less, the hypothesis that $P \geq 25\%$ is rejected with an actual error rate of 0.197. Sample size estimates were determined using PASS v. 19.0.2 (NCSS, LLC, Kaysville, UT).

Table 15: PASS Output Single-Stage Phase II Clinical Trials Analysis

Design for Testing $H_0: P \leq P_0$ versus $H_1: P \geq P_1$							
P_0	P_1	Alpha	Beta	Cut-Off $R + 1$	N	Actual Alpha	Actual Beta
0.05	0.25	0.050	0.2	3	16	0.04	0.197
Report Definitions							

P_0 is the maximum response proportion of a poor drug.P_1 is the minimum response proportion of a good drug.N is the sample size.If the number of responses $\geq R+1$, P_0 is rejected.If the number of responses $\leq R$, P_1 is rejected.Alpha is the probability of rejecting that $P \leq P_0$ when this is true.Beta is the probability of rejecting that $P \geq P_1$ when this is true.							

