14.3. Statistical Analysis Plan

The primary goal of the study is to evaluate the effectiveness of the poly-ICLC. Based on the single stage design, response of the drug will be determined after 16 participants are evaluable for the primary endpoint assessment. Participants will be classified based on response (CR/PR vs. MR/SD/PD). If at least 3 of 16 participants respond to treatment, the hypothesis that $P \leq 5\%$ is rejected at alpha = 0.05 and accept that the higher rate of P greater or equal to 25% is more likely; otherwise, the drug will be deemed ineffective based on having an objective response rate

not significantly different than the objective response rate of a poor drug. Comparison between RANO and RAPNO response criteria will be descriptive only.

Key secondary outcomes will be examined at baseline including clinical, quality of life and visual function. Following complete accrual, study enrollment and completion will be summarized as per a Consort Diagram with reasons for withdrawal or unable to complete the study. Appropriate data analysis sets will be defined as follows. The full-analysis set will include data from all participants who receive ≥ 1 dose of therapy on this study; a safety analysis set will comprise data from participants in the full-analysis set with any treatment doses. Other data sets (responding, evaluable) will be defined and will include data from participants who have the necessary baseline and on-study measurements to provide interpretable results for specific parameters of interest.

Descriptive summaries will be prepared to show sample size, mean, standard deviation, 95% confidence intervals (CIs) median, minimum, and maximum for continuous variables and counts, percentages, and 95% CIs for categorical variables.

For endpoints relating to tumor control, participant well-being, and biomarkers, analyses will be done based on the full analysis, responding, evaluable data sets, as appropriate. Time-to-event analyses will be performed with reference to the date of first treatment on this study. Analyses will focus on evaluation of outcomes and will be largely descriptive. Changes in tumor volumes will be summarized by medians, ranges, and the corresponding 95% CI.

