Based on the safety analysis set, information regarding study treatment administration, drug dosing and cycle compliance, safety variables, will be described and summarized. Data from the biological analysis will also be described and summarized. Safety will be assessed via tabulations of AEs and SAEs as well as Diary recordings following treatment dose/cycle of therapy.

All analyses for outcome results will be based on evaluable participants, as defined in section 14.

At the end of the trial, we will report poor performance if the treatment is rejected when not meeting the criteria of at least 3 responders' cases. If there is no success, we will report a failure to reject the null hypothesis. If the null hypothesis is rejected, the probability of the estimated success rate will be reported and 95% confidence intervals as well as the distribution of changes in tumor size.

Dose-limiting toxicity (DLT) is not an objective in this trial. Toxicity will be continuously monitored.

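### Dosed patients with no follow-up scan leave the primary response denominator, which could raise the false-positive rate from 0.043 to about 0.074 at most if they are all non-responders

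*Combined protocol and SAP*

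**What the plan says.** Section 14 (Primary Endpoints) sets two conditions: patients are "evaluable for response if they have received at least one dose of treatment and have at least one post-baseline tumor assessment". Section 14.3 adds: "All analyses for outcome results will be based on evaluable participants, as defined in section 14". The decision rule in Sections 14.2 and 14.3 is 3 or more responders among 16 evaluable participants. Section 14.2 covers losses by over-enrolment: "To allow for 25% unevaluable participants, a maximum of up to 20 participants will be enrolled".

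Section 14.3 also defines a wider set: "The full-analysis set will include data from all participants who receive" one or more doses. It then allows tumor-control endpoints to use the full, responding or evaluable set as suits the endpoint, without saying which one carries the primary test. The primary classification is CR/PR against MR/SD/PD, which leaves no place for a dosed patient without a scan. No sensitivity analysis in all treated patients is planned.

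The first scheduled response scan is at the end of cycle 3 (Protocol Summary; Section 5.2; Appendix 3), that is 3 x 28 days = 12 weeks, give or take 2 weeks.

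**The concern.** Evaluability is settled after treatment has begun and may depend on how the patient fares. In the first 12 weeks a patient can die, be lost, withdraw consent or start new tumor-directed therapy, and Section 3.5 makes each of these an off-study event. Section 10.4 foresees symptomatic deterioration without objective progression, and asks for imaging after clinical progression only where feasible. An early treatment failure can thus be recorded as unevaluable when it should count as a non-response.

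The rule turns on three responders, so a few exclusions matter. Three of 16 is 18.75% and passes; the same three among 20 treated is 15%. If those excluded respond less often than those scanned, the reported response rate is too high for the treated population. A drug with a 5% response rate among treated patients would then pass more often than the plan states.

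**Working it through.** **Inputs.** Section 14.2: null rate 5%, target rate 25%, nominal alpha 0.05, 16 evaluable, cutoff 3, stated actual alpha 0.043 and beta 0.197, at most 20 enrolled. The documents do not say how many of the up to 4 extra patients would be dosed but unscanned, or how such patients would respond. Both are treated as assumptions below.

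**1. The plan's own figures.** With X binomial(16, p):
- P(X >= 3 | p = 0.05) = 1 - (0.4401 + 0.3706 + 0.1463) = 0.043.
- P(X >= 3 | p = 0.25) = 0.803, so beta = 0.197.

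Both match Section 14.2.

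**2. Missing scans unrelated to response.** The rate among evaluable patients stays 5%, so alpha stays 0.043 however many are dropped.

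**3. Every unscanned patient a non-responder.** Let T be the number treated, with 16 evaluable and a true rate of 5% among all T. The rate among evaluable patients is 0.05 x T/16. As a cross-check, the last column gives the chance of 3 or more responders among all T at 5%.

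| T treated | Rate among evaluable | P(>= 3 of 16) | P(>= 3 of T at 5%) |
|---|---|---|---|
| 16 | 0.0500 | 0.0429 | 0.0429 |
| 17 | 0.0531 | 0.0500 | 0.0503 |
| 18 | 0.0563 | 0.0575 | 0.0581 |
| 19 | 0.0594 | 0.0656 | 0.0665 |
| 20 | 0.0625 | 0.0742 | 0.0755 |

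One such patient brings alpha to about 0.05; two or more are needed to pass it.

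**4. In between.** With 20 treated and 4/20 = 20% unscanned, let q be the response rate among the unscanned. The evaluable rate is (0.05 - 0.2q)/0.8. For q = 0, 1.25%, 2.5%, 3.75% and 5%, alpha is 0.074, 0.066, 0.058, 0.050 and 0.043.

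**5. The ceiling.** With 16 evaluable and a cap of 20, the unscanned share cannot exceed 20%. A 25% share would need 16/0.75 = 21.3 treated. The plan's 25% corresponds to 16 x 1.25 = 20, which is 20% of those enrolled.

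**6. Decision rules on treated patients, no scan = non-responder.**

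| Denominator | Cutoff | Alpha at 5% | Power at 25% |
|---|---|---|---|
| First 16 treated | 3 | 0.043 | 0.803 |
| 20 treated | 3 | 0.0755 | 0.909 |
| 20 treated | 4 | 0.016 | 0.775 |

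If 25% holds only among scanned patients and 20% are unscanned, the all-treated rate is 0.25 x 0.8 = 20%, and the first-16 rule has power of about 0.65.

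**The case against.** A reader might infer that every patient who stops early is dropped. The documents do not support that:
- Section 5.3 and Appendix 3 call for an MRI at the end of therapy, and Appendix 3 also at progression.
- Section 3.5 keeps patients in follow-up after they stop therapy, and Section 5.4 schedules MRIs every 3 months in the first year off therapy.
- Section 14 counts assessments made after withdrawal from protocol therapy.
- Section 10.4 asks for every effort to document progression after symptomatic deterioration.

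A patient who stops for toxicity and then has the off-therapy MRI is evaluable. The gap is therefore narrower: patients who die, are lost, withdraw consent or start new therapy before any scan. None of these provisions closes it, because none counts an unscanned dosed patient as a non-responder.

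Three further points are fair. The 0.043 is correct for the evaluable population that the plan tests; judging it against a 5% rate among all treated changes the target population. Some of the allowance may be never-dosed patients, who do not affect the error rate among the treated, although Section 3.3.3 places enrolment after confirmed eligibility and within 7 days of treatment. And the CONSORT diagram in Section 14.3 will show withdrawals and their reasons, though showing exclusions does not alter the test.

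**Conclusion.** As written, the plan removes dosed patients with no post-baseline scan from the primary denominator and does not assign the primary test to the full-analysis set. This can bias the response rate upward. The false-positive rate among treated patients lies between 0.043 (missing scans unrelated to response) and about 0.074, or 0.0755 on the all-treated count (20 treated, four unscanned, all non-responders).

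A reader might infer that the rule does push the error above 5%. The documents do not show this: it needs about two or more dosed, unscanned patients and a clearly lower response rate among them, and neither is given. Nor can a figure for 25% unscanned be used, since the enrolment cap rules it out with 16 evaluable. The point is a conditional bias worth removing in advance; the stated alpha is not an arithmetic error.

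**What to change.** - In Section 14.3, prespecify the objective response rate in the full-analysis set: at least one dose, with no post-baseline scan counted as non-response, and an exact 95% confidence interval. Report it beside the evaluable rate, and require any success claim to quote both.
- Reconcile the sentence in Section 14.3 that leaves the choice of analysis set open with the later one that restricts outcome analyses to evaluable participants. Name the set that carries the primary test.
- If the formal decision moves to treated patients, fix the denominator in advance. The first 16 treated with cutoff 3 keeps the present alpha and, if 25% holds among all treated, the present power. Using all 20 treated requires cutoff 4, because cutoff 3 has alpha 0.0755.

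**Cost.** Reporting both rates changes wording only and adds no visits; the all-treated rate will be the same or slightly less favourable. Moving the formal test costs some power: about 0.65 for the first-16 rule if 25% holds only among scanned patients and 20% are unscanned, or 0.775 for 4 of 20. Restoring 80% with cutoff 4 would take 21 treated (alpha 0.019, power 0.808), one above the present cap.
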